#### 6.4.2 Laboratory Tests

Laboratory tests are analyzed using results from the external central laboratory **CCI** [REDACTED] which identifies expired kits, and from local laboratory tests reported on CRFs. The central laboratory reports both laboratory collection date and time, whereas CRFs capture only laboratory collection date.

Laboratory tests of clinical interest are collected at the following visits:

- Hematology: Screening; Pre-Baseline; Weeks 4, 24, and 52; and early termination.
- Serum chemistry (including LFTs and lipids): Screening; Pre-Baseline; Weeks 4, 24, and 52; and early termination. Exceptions are for the following:
  - LFTs (ALT, AST, ALP, TBL, direct bilirubin, indirect bilirubin): Screening; Pre-Baseline; all visits during the treatment period; early termination; and Follow-up Week 2.
  - Lipids (total cholesterol, high-density lipoprotein [HDL] cholesterol, low-density lipoprotein [LDL] cholesterol, triglycerides): Pre-Baseline; Weeks 24 and 52; and early termination.
- Urinalysis: Pre-Baseline; Week 52; and early termination.

Clinically significant laboratory abnormalities are identified as grade 3 to 4 laboratory test results. Refer to the Zavegeptan Core SAP for laboratory tests of clinical interest for analyses, including identification of those with toxicity grades.

The following by-subject laboratory test listings are provided for the enrolled analysis set:

- Select laboratory test groups: hematology (both SI and US units)\*; serum chemistry, including LFTs (both SI and US units)\*; urinalysis (US units only)\*; pregnancy (US units only)\*; endocrinology, serology, drug screen, and miscellaneous laboratory tests (US units only). The pregnancy listing identifies positive pregnancy tests, which are defined as serum or urine pregnancy tests with either (a) “positive” character value, or (b) numeric value  $\geq 25$  U/L.
- LFT values and ratios to ULN (i.e., ALT, AST, TBL and ALP) for both US and SI units\*. The listing displays all LFT results over time for subjects with select LFT elevations (ALT or AST  $> 3$  x ULN; ALP or TBL  $> 2$  x ULN) at any time point.

- Creatine kinase (CK) elevation questionnaire.

Listings display toxicity grades and identify expired kits from the central laboratory, if applicable, and those marked with “\*” display COVID-19 visit impact code for visits impacted by COVID-19 (see Section 9.1.5.2). Refer to the Zavegeptan Core SAP for listing contents.

#### **6.4.2.1      *Laboratory Test Abnormalities***

On-treatment laboratory test abnormalities are tabulated as the number and percentage of subjects in the safety analysis set in the following frequency tables:

- Worst (highest) on-treatment laboratory test abnormality for each graded laboratory test \*.  
Grade 3 to 4 results support the primary objective.
- Laboratory test toxicity grade shift from baseline to the worst on-treatment toxicity grade for each graded laboratory test.
- Laboratory test low/normal/high shifts from baseline to any abnormal on-treatment value for each laboratory test with normal ranges.

Refer to the Zavegeptan Core SAP for toxicity grade categories and additional details.

Endpoints marked with “\*” are also tabulated (1) on treatment by subgroup level and overall for all subgroups of interest specified in Section 4.3 for the safety analysis set, and (2) during follow-up for the follow-up analysis set.

#### **6.4.2.2      *Liver Function Test Elevations***

Refer to the Zavegeptan Core SAP for additional details.

#### **LFT Elevations: Cumulative, Mutually Exclusive, and Composite**

LFT elevations are based on fold changes above ULN. The number and percentage of subjects with LFT elevations are tabulated separately for the following each analysis periods and analysis sets:

- Pre-treatment for the enrolled analysis set
- Pre-treatment for the safety analysis set
- On-treatment for the safety analysis set
- Follow-up for the follow-up analysis set.

#### **LFT ULN Shifts from Baseline to Worst Elevation**

LFT ULN shifts from baseline to the worst (highest) on-treatment LFT elevation are tabulated as the number and percentage of subjects in the safety analysis set in pre-specified elevation categories.

## Exposure-adjusted Cumulative LFT Elevations

Exposure-adjusted cumulative on-treatment LFT elevations are tabulated. Calculations set the reference start date to the study drug start date, reference end date to the study drug end date, and reference last date to the study drug last date + 7 days.

### Time to LFT Elevations

The number and percentage of subjects in the safety analysis set with time to first on-treatment LFT elevations (ALT > 3x ULN; AST > 3x ULN; ALT or AST > 3x ULN) are presented for subjects with on-treatment LFT elevations in the following categories: ≤ 2, > 2 to ≤ 4, > 4 to ≤ 8, ..., > 48 to ≤ 52, > 52 weeks. Time to elevation is calculated as (LFT collection date – study drug start date + 1)/7.

### LFT Plots

An evaluation of drug-induced serious hepatotoxicity (eDISH) scatter plot displays the maximum TBL ratio of value to ULN on the y-axis versus the maximum ALT ratio of value to ULN on the x-axis by treatment group, where both maxima are on treatment but not necessarily concurrent.

By-subject longitudinal LFT plot displays ratios of values to ULN for AST, ALT, ALP, and TBL on the y-axis versus study week of the laboratory test result on the x-axis for subjects in the safety analysis set with any of the following LFT elevations in any safety analysis period: ALT > 3x ULN; AST > 3x ULN; TBL > 2x ULN; ALP > 2x ULN. Study weeks are defined as study day/7, where study day is derived from the laboratory test collection date (see Section 7.3). Each figure also displays treated migraine days using symbols along the x-axis (see Section 6.4.6), and denotes additional study milestones (e.g., start of the on-treatment safety analysis period, and start of the follow-up safety analysis period) using vertical lines with their corresponding descriptions in footnotes.

#### 6.4.2.3 *Laboratory Test Changes from Baseline*

Values and changes from baseline in hematology and serum chemistry laboratory tests are tabulated descriptively as continuous variables at baseline and each scheduled visit in the on-treatment and follow-up safety analysis periods.

If a subject has multiple values in an analysis visit window in a safety analysis period, then a single value is selected using the following hierarchy as available:

- Non-missing viable value collected closest to the target date for the visit. In the case of a tie, the last non-missing viable value collected is used. If there are multiple viable values on the same date, then the following hierarchy is used as available:
  - Last central laboratory test value collected timewise with the last accession identifier.
  - Last local laboratory test value entered.

Viable laboratory test values are defined as those from (1) kits from the central laboratory that are not expired (see Section 6.4.2), or (2) local laboratory tests reported on CRFs.

- Non-missing value from an expired kit from the central laboratory collected closest to the target date for the visit. In the case of a tie, the last non-missing value collected with the last accession identifier is used.

Results are also summarized at the EOT visit with a single value in the on-treatment safety analysis period using the following hierarchy as available:

- Last non-missing viable value collected. See above for handling multiple viable values on the same date.
- Last non-missing value collected with the last accession identifier from an expired kit from the central laboratory.

### **6.4.3      *Vital Signs and Physical Measurements***

All parameters are reported with measurement date only (no time).

Vital signs include systolic blood pressure, diastolic blood pressure, heart rate, temperature, and respiratory rate. These parameters are measured at Screening, Pre-Baseline, every visit during the treatment period, early termination, and Follow-up Week 2.

Physical measurements include height (measured at Screening only), weight, and BMI.

A by-subject listing of vital signs and physical measurements is provided for the enrolled analysis set, and displays COVID-19 visit impact code for visits impacted by COVID-19 (see Section 9.1.5.2).

#### **6.4.3.1      *Vital Sign and Physical Measurement Changes from Baseline***

Values and changes from baseline in vital signs and physical measurements are tabulated descriptively as continuous variables at baseline and each scheduled visit in the on-treatment and follow-up safety analysis periods for the safety analysis set.

If there are multiple values on the same measurement date, then the last value entered is used.

#### **6.4.3.2      *Vital Sign and Physical Measurement Abnormalities***

On-treatment vital sign and physical measurement abnormalities are tabulated as the number and percentage of subjects in the safety analysis set in categories specified in the Zavegept Core SAP.

Follow-up vital sign and physical measurement abnormalities are tabulated analogously for the follow-up analysis set.

#### **6.4.4      *Electrocardiogram***

ECG parameters include RR, QRS, PR, QT, QTcB, QTcF, and ventricular heart rate. ECGs are measured with both acquisition date and time by the external source **CCI** at the following visits: Screening; Weeks 4, 24, and 52; early termination; Follow-up Week 2.

A by-subject listing of ECG results is provided for the enrolled analysis set, and displays COVID-19 visit impact code for visits impacted by COVID-19 (see Section [9.1.5.2](#)).

##### **6.4.4.1      *ECG Changes from Baseline***

Values and changes from baseline in ECG intervals (e.g., RR, QRS, PR, QT, QTcB, QTcF) and ventricular heart rate are also tabulated descriptively as continuous variables at baseline and each scheduled visit in the on-treatment and follow-up safety analysis periods for the safety analysis set.

If there are multiple values on the same acquisition date and time, then the value with the last ECG requisition identifier is used.

##### **6.4.4.2      *ECG Interpretation Shifts from Baseline to Worst Category***

ECG interpretation shifts from baseline to the worst on-treatment category are tabulated as the number and percentage of subjects with normal, abnormal, and clinically significant abnormal interpretations for the safety analysis set.

##### **6.4.4.3      *ECG Abnormalities***

On-treatment ECG abnormalities are tabulated as the number and percentage of subjects in the safety analysis set in the categories specified in the Zavegeptan Core SAP.

Follow-up ECG abnormalities are tabulated analogously for the follow-up analysis set.

ECG abnormalities are presented together with vital sign and physical measurement abnormalities in the same tables (see Section [6.4.3.2](#)).

#### **6.4.5      *S-STS***

The S-STS is a prospective rating scale that contains 16 patient-reported questions and 6 clinician-reported questions to track both treatment-emergent suicidal ideation and behaviors.

Refer to the Zavegeptan Core SAP for calculation of the S-STS ideation subscale, behavior subscale, and total scores.

Values and changes from baseline in the self-reported S-STS ideation subscale, behavior subscale, and total score are tabulated descriptively as continuous variables at baseline and the worst (highest) score in safety analysis periods. The table also presents the number and percentage of subjects in the worst (highest) score change from baseline category (i.e., < -1, -1,

no change, 1, > 1) in safety analysis periods for the ideation subscale, behavior subscale, and total score.

Results are tabulated on-treatment for the safety analysis set, and follow-up for the follow-up analysis set.

A by-subject listing of S-STS is provided for the enrolled analysis set, and displays COVID-19 visit impact code for visits impacted by COVID-19 (see Section 9.1.5.2).

Refer to the Zavegeptan Core SAP for the listing contents.

#### **6.4.6 Migraine Days per Month**

Subjects report migraine status (yes, no, unable to recall) and intensity (mild, moderate, severe, unable to recall) every day in the eDiary evening report. Sites may provide these data on the eDiary medication reconciliation form.

Migraine days per month are assessed as “migraine days per 4 weeks” to correspond with the 4-week visit schedule. Analyses are based on the OP and LTT analysis periods for the migraine analysis set, i.e., subjects in the safety analysis set with  $\geq 14$  days of data (not necessarily consecutive) in both the OP analysis period and  $\geq 1$  month (4-week interval) in the LTT analysis period.

- A day of data is defined as an eDiary record with complete date and {yes or no} response to having a migraine. If a subject has multiple responses or migraine severities on the same date, then the most severe migraine last sequenced is chosen. Only days of data are included in analyses.
- A migraine day is defined as a day of data with a “yes” response to having a migraine.
- A treated migraine day is defined as a migraine day on which zavegeptan is administered.
- Months are defined as 4-week (28-day) intervals in the LTT analysis period. See Section 6.2.6.1 for the definition of months.

Thus, the total numbers of days of data and migraine days are calculated for the OP analysis period and for each month in the LTT analysis period.

##### **6.4.6.1 Migraine Days per Month over Time**

Tables present results separately for the (1) migraine analysis set, and (2) migraine analysis set taking concomitant prophylactic migraine medication (see Section 6.2.5.2).

The number of migraine days per month in the LTT period is examined relative to the number of migraine days per month in the OP by migraine intensity (total [mild, moderate, severe, unable to recall, not reported]; moderate or severe). The following tables are produced:

- Values and changes (both absolute and percent) from the OP in the number of migraine days per month by month during LTT and in the overall LTT summarized descriptively as continuous variables by migraine intensity (including 2-sided 95% normal CIs for mean

change). The number of migraine days per month are prorated to 28 days and derived as follows:

- OP:  $28 \times (\text{total number of migraine days in the OP analysis period}) / (\text{total number of data days in the OP analysis period})$ .
- Month during LTT:  $28 \times (\text{total number of migraine days in the month}) / (\text{total number of data days in the month})$ . In addition, subjects must have  $\geq 14$  days of data (not necessarily consecutive) in a month to be evaluable for that month.
- Overall LTT:  $28 \times (\text{total number of migraine days in the LTT analysis period}) / (\text{total number of data days in the LTT analysis period})$ .
- Number and percentage of subjects with  $\leq 0\%$ ,  $\geq 25\%$ ,  $\geq 50\%$ ,  $\geq 75\%$ , and  $100\%$  reduction from the OP in the number of migraine days per month by month during LTT and during overall LTT by migraine intensity.

The following plots are produced for the migraine analysis set:

- Scatter plot of change from OP in the number of total migraine days per month in the overall LTT on the y-axis versus number of total migraine days per month in the OP on the x-axis
- Scatter plot of percent change from OP in the number of total migraine days per month in the overall LTT on the y-axis versus number of total migraine days per month in the OP on the x-axis
- Scatter plot of change from OP in the number of moderate or severe migraine days per month in the overall LTT on the y-axis versus number of moderate or severe migraine days per month in the OP on the x-axis
- Scatter plot of percent change from OP in the number of moderate or severe migraine days per month in the overall LTT the y-axis versus number of moderate or severe migraine days per month in the OP on the x-axis
- Longitudinal plot of mean change from OP in the number of total migraine days per month on the y-axis versus month on the x-axis
- Longitudinal plot of mean change from OP in the number of moderate or severe migraine days per month on the y-axis versus month on the x-axis.

Scatter plots display a horizontal reference line at 0. Longitudinal plots display error bars denoting 95% CIs.

In the percent change/reduction analyses, subjects must also have  $\geq 1$  migraine day (absolute not prorated) of appropriate migraine intensity during the OP to be included.

A by-subject listing presents migraine attacks and intensity over time for the enrolled analysis set, and displays COVID-19 visit impact code for visits impacted by COVID-19 (see Section 9.1.5.2).

Another by-subject listing presents the number of migraine days per month during the OP, overall LTT, and by month during the LTT for the safety analysis set.

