5.2 Inclusion Criteria

- 1) Signed written informed consent. Written informed consent must be obtained from the subject in accordance with requirements of the study center's institutional review board (IRB) or ethics committee, prior to the initiation of any protocol-required procedures.
- 2) Subjects must agree to provide all requested demographic information (i.e. gender, race).
- 3) Subjects must be able to read and understand English or Spanish.
- 4) Target Population: Subjects with minimum 1 year history of migraine (with or without aura) consistent with a diagnosis according to the International Classification of Headache Disorders, 3rd Edition¹, including the following:
 - a) Migraine attacks present for more than 1 year with the age of onset prior to 50 years of age.
 - b) Migraine attacks, on average, lasting about 4 72 hours if untreated.
 - c) 2-8 migraine attacks of moderate or severe intensity per month within last 3 months prior to the screening visit.
 - d) Subjects must be able to distinguish migraine attacks from tension/cluster headaches.
 - e) Treatment of 2 or more migraines attacks with standard of care medication during Observation Phase.
 - f) Less than 15 days with headaches (migraine or non-migraine) per month in each of the 3 months prior to the screening visit and during the observation phase.

- g) Subjects on prophylactic migraine medication are permitted to remain on therapy if they have been on a stable dose for at least 3 months prior to screening visit, and if the dose is not expected to change during the course of the study.
- h) Subjects with contraindications for use of triptans may be included provided they meet all other study entry criteria.

5) Age and Reproductive Status:

- a) Male and Female subjects ≥18 years of age.
- b) All subjects must understand the contraception requirements for this study and agree to use two acceptable methods of contraception to avoid pregnancy throughout the study in such a manner that the risk of pregnancy is minimized. See Section 5.6 for the definition of WOCBP and contraception requirements.
- c) Women must not be pregnant, lactating or breastfeeding.
- d) At the pre-baseline visit prior to dispensing study drug, WOCBP must have a negative pregnancy test.

6) Other Inclusion Criteria:

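### The mean of per-subject percent changes in migraine days is biased upward and can show a spurious increase beside an absolute decrease in the same SAP 6.4.6.1 table

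*SAP*

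**What the plan says.** SAP 6.4.6.1 summarises "Values and changes (both absolute and percent) from the OP in the number of migraine days per month by month during LTT" and for the overall LTT as continuous variables, for total and for moderate or severe days, "including 2-sided 95% normal CIs for mean" change. The OP value is the number of OP migraine days divided by the number of OP data days, times 28. The OP lasts 28 ± 2 days (Protocol 4.3.1), and the migraine analysis set needs only 14 days of OP data (SAP 4.1).

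The section's one restriction on the denominator is this: "In the percent change/reduction analyses, subjects must also have" at least one "migraine day (absolute not prorated) of appropriate migraine intensity during the OP to be included".

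Three inclusion criteria in Protocol 5.2 shape the OP count:

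- 4c: "2-8 migraine attacks of moderate or severe intensity per month within last 3 months prior to the screening visit". This counts attacks, not days.
- 4e: "Treatment of 2 or more migraines attacks with standard of care medication during Observation Phase". SAP 9.2 checks this in days: 0 or 1 treated migraine day is a deviation.
- 4f: "Less than 15 days with headaches (migraine or non-migraine) per month in each of the 3 months prior to the screening visit". The criterion goes on to cover the observation phase too.

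Neither document gives a mean, a standard deviation or a distribution of migraine days.

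**The concern.** A small, noisy count is a poor denominator. Take two subjects whose usual rate is 4 days per 28, both with 4 days in an LTT month. One happened to have 2 days in the OP and the other 6. Their absolute changes are +2 and −2, which average 0. Their percent changes are +100% and −33%, which average +33%. Losses stop at −100%, while gains have no comparable limit. A larger sample only narrows the interval around this displaced value.

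The table reports the exploratory objective on reduction from the OP. A reader could meet a mean percent increase whose interval lies above 0 beside a mean absolute decrease whose interval lies below 0, in subjects whose underlying rate never moved.

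**Working it through.** The plan gives no expected percent change, standard deviation or power for migraine days, so there is no figure of its own to reproduce on this point. Every size below rests on assumed rates, with no true change throughout.

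**1. The bias in isolation.** Let every subject have rate μ per 28 days, with OP count X ~ Binomial(28, μ/28) and LTT expectation μ. The expected mean percent change is μ × E[1/X | X ≥ k] − 1, where k is the lowest OP count admitted.

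| μ | k = 1 | k = 2 |
|---|---|---|
| 3 | +28.3% | −1.2% |
| 4 | +28.5% | +10.2% |
| 5 | +24.0% | +14.5% |
| 6 | +19.1% | +14.8% |
| 8 | +11.9% | +11.2% |

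For μ = 4 and k = 1, P(X = 0) = (24/28)^28 = 0.0134, so the mean OP count among those included is 4/(1 − 0.0134) = 4.05. The absolute change is 4 − 4.05 = −0.05 day and the ratio of means is 4/4.05 − 1 = −1.3%. The mean of ratios is 4 × 0.3213 − 1 = +28.5%.

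Column k = 1 uses only the SAP floor. Column k = 2 is what 4e implies at the least for total days. Selecting on a minimum OP count also brings in regression to the mean, which pulls the other way and dominates at low rates.

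**2. With the entry rules applied.** Simulation with N = 600, rates uniform on 2 to 8 days per 28, overall LTT of 13 months, at least 2 treated OP migraine days, fewer than 15 OP days, and 75% of days moderate or severe. Brackets give the share of simulated trials with the 95% interval wholly above 0 (percent) or wholly below 0 (absolute).

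| Days, share treated | Mean % change | Absolute change (days) | Ratio of means | Median % |
|---|---|---|---|---|
| Total, 100% | +9.2 (1.00) | −0.19 (0.67) | −3.6% | −2.0 |
| Total, 80% | +5.7 (0.92) | −0.29 (0.94) | −5.3% | −4.2 |
| Total, 60% | +1.7 (0.16) | −0.45 (1.00) | −7.7% | −6.9 |
| Mod./severe, 100% | +18.0 (1.00) | −0.15 (0.52) | −4.4% | −2.3 |
| Mod./severe, 80% | +14.7 (1.00) | −0.22 (0.81) | −5.8% | −4.3 |
| Mod./severe, 60% | +10.1 (0.99) | −0.33 (0.99) | −8.0% | −6.8 |

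**3. Other rate distributions.** With gamma-distributed rates (mean 4 to 6, variance 2 to 8), Poisson counts, N = 600 and 60–80% of days treated:

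- Moderate or severe days: about +5% to +21%, beside an absolute change of about −0.1 to −0.5 day.
- Total days: about −4% to +12%.

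At mean 5 and 80% treated, moderate or severe days give +13% to +17% with a half-width of about 6 points, so the lower limit is at least 13 − 6 = +7%. The absolute change is −0.24 to −0.28 day with a half-width of about 0.16, so the upper limit is at most −0.24 + 0.16 = −0.08 day. The two intervals exclude 0 in opposite directions.

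**4. Where it weakens or reverses.** If every subject has rate 3 (80% treated, N = 600), the overall-LTT means are −6.9% for total days and +1.0% for moderate or severe days. In a subset of 100, an assumed size for subjects on prophylactic medication, the total-days interval lies above 0 in only 3% to 75% of trials. Extra month-to-month variation works the other way: with rates uniform on 3 to 12 it raises the total-days mean to +15% to +19%.

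**The case against.** The analysis is exploratory and descriptive, in a safety trial with no efficacy section. No test is planned. SAP Table 2 defines this endpoint as values and changes in days and does not name percent change, and the longitudinal mean plots show change in days only. Descriptive statistics are left to the Core SAP, which is not among the documents, so medians and quartiles may already be produced. Scatter plots of percent change against the OP count would show inflation at low counts. Migraine-day outputs are left out of the interim report that supports the drug application. All of this stands and limits the consequence. None of it removes the biased mean and its interval from the final report's table.

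Three stronger readings are tempting, and the documents do not support them:

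- A reader might infer that the table will show a significant increase of roughly 12% to 28% for both intensities. That range needs the one-day floor alone and assumed rates of about 3 to 8 days. Criterion 4e removes most low total counts, and the total-days mean can then be near 0 or negative.
- A reader might infer that the absolute change is the unbiased answer. It is not: selection on the OP produces an apparent reduction with no change in rate, and part of the contradiction comes from that row.
- A reader might call the responder rows defective because all worsening is pooled at 0% or below. The objective concerns reduction, so this is a reporting preference.

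**Conclusion.** The concern holds as a risk, not a certainty. The mean of individual percent changes over a single OP count is biased upward, and its normal interval is centred on the wrong value. Under the gamma-rate assumptions in step 3, the interval for moderate or severe days lies above 0 in most scenarios; at the bottom of the range, about +5% with a half-width near 5.6 points, it reaches 0. For total days it often includes 0. The opposite-direction result is clearest for moderate or severe days, because 4e counts treated migraines of any intensity and so sets no floor of 2 on that row.

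These sizes also assume complete diaries, no dropout, independent days within subject, and a treated day standing in for a treated attack. Multi-day attacks would make 4e bind more strongly. The actual size cannot be known until the OP distribution is seen.

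**What to change.** In SAP 6.4.6.1:

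- For percent change, report the percent change in the group mean, mean LTT / mean OP − 1, with a bootstrap interval (resampling subjects) or a delta-method interval that allows for the within-subject correlation. Compute it on the same subjects as the absolute change. It then equals mean change / mean OP and must agree with it in sign.
- Report the median and quartiles of individual percent change, keeping the present floor, and drop the normal interval for their mean. If the Core SAP already supplies the median and quartiles, say so here.
- Add a footnote that the absolute change and the ratio of means still include regression to the mean, because subjects are selected on OP migraines (inclusion 4e and 4f). In the simulations above this alone gave ratios of means of −3.6% to −8.0%.
- Optionally, add rows for increases of at least 25% and at least 50%.

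The cost is SAP wording and a small change to one table program. No new data are needed, and the absolute-change summaries stay in place.
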